8.1.2. Assessment of moderate/severe COPD exacerbations

Moderate/ severe exacerbations of COPD will be recorded based on the clinical evaluation.

A moderate/ severe COPD exacerbation is defined as a sustained worsening of respiratory symptoms that requires treatment with systemic corticosteroids, antibiotics (moderate), or hospital admission (or any combination thereof). Events are classified as moderate or severe according to the European Medicines Agency Guideline 2012. Moderate exacerbations are those that require treatment with additional rescue bronchodilators systemic corticosteroids and/or antibiotics. Severe exacerbations are defined as those requiring treatment with additional rescue bronchodilators systemic corticosteroids and/or antibiotics. Hospital admission, or resulting in death.

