8.1. Efficacy Assessments

At each follow-up visit, participants will be questioned about any hospitalizations or any unexpected medical events, particularly moderate exacerbations treated with antibiotics and/or steroids and all information will be collected on the eCRF. In addition, the participant's medical records will be reviewed and details of any relevant medical events and any medication prescribed will be recorded in the eCRF. Participants will also be contacted by telephone each month between the study visits (by the clinical investigator or by a research staff member) to assess this information.

An emergency telephone number contact will be set up in each center, in case the patients require hospitalization, particularly for acute exacerbations of respiratory symptoms.

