7.2 Analysis of secondary efficacy endpoints

Definitions and data conventions

Number of re-hospitalizations and death

The number of re-hospitalizations and deaths will be calculated per-subject as the sum of the number of hospitalizations as recorded in the ‘COPD Exacerbation Form’ and the deaths (all cause).

Number of moderate/severe COPD exacerbations

The number of moderate/severe COPD exacerbations will be calculated per-subject as the sum of the number of COPD exacerbations recorded as “Moderate” or “Severe” in the ‘COPD Exacerbation Form’.

Number of pneumonia events

The number of pneumonia events will be calculated per-subject as the sum of adverse events classified with the following System Organ Classes/Preferred Terms:

System Organ Class	Preferred Term
Respiratory, thoracic and mediastinal disorders	
 • Pneumonia NOS • Acute pneumonia • Lung infection • Multilobar pneumonia • Bronchopneumonia • Pneumonia lobar • Pneumonia, organism unspecified • Bronchopneumonia NOS • Acute bronchopneumonia • Community acquired pneumonia • Lobar pneumonia NOS • Ventilator associated pneumonia • Healthcare associated pneumonia • Pneumonia recurrent • Bronchopulmonary infection

Forms			
Title	Statistical Analysis Plan Template		
Code	Version	Effective Date	Page
FRM_ST03_032	02	02 Oct 2017	20 of 26

	
 Pulmonary suppuration Lung infection NOS Pleuropneumonia Bronchopneumonia, organism unspecified Bilateral bronchopneumonia Infectious pneumonitis Nosocomial pneumonia Bronchial pneumonia Bilateral pneumonia Hospital acquired pneumonia Right middle lobe pneumonia Lobar pneumonia
--	---

Number of acute cardiac events

The number of acute cardiac events will be calculated per-subject as the sum of adverse events classified with the following System Organ Classes/Preferred Terms:

System Organ Class	Preferred Term
Cardiac disorders	
 Heart failures -Coronary artery disorders Cardiac arrhythmias Embolic stroke Haemorrhagic stroke Thrombotic stroke

Time on study

Time on study (years) will be calculated using the following formula:

Time on study (years) = (Date of patient completion or withdrawal - Date of randomization +1)/365.25.

Log-time on study (years)

The log-time on study in years will be calculated using the following formula:

$$\text{Log-time on study} = \ln(\text{time on study})$$

Statistical analysis

Analysis will be performed on the ITT population.

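### Protocol 8.1.2 states the moderate/severe exacerbation definition inconsistently, so reliever-only episodes could, but need not, enter a secondary endpoint that the SAP counts by site label

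*Protocol*

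**What the plan says.** The number of moderate/severe COPD exacerbations is the first secondary endpoint listed in Protocol section 3 and in SAP 3.5.2.

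Protocol 8.1.2 opens with the recording basis: "Moderate/ severe exacerbations of COPD will be recorded based on the clinical evaluation". An event is then "defined as a sustained worsening of respiratory symptoms that requires treatment with systemic corticosteroids, antibiotics (moderate), or hospital admission (or any combination thereof". The section next refers the grading to a 2012 European Medicines Agency guideline and writes out both grades. For moderate: "Moderate exacerbations are those that require treatment with additional rescue bronchodilators systemic corticosteroids and/or antibiotics". For severe: "Severe exacerbations are defined as those requiring treatment with additional rescue bronchodilators systemic corticosteroids and/or antibiotics". Admission and death follow the severe sentence as a separate fragment with no verb of its own.

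Protocol 8.1 tells sites to ask about hospitalisations and unexpected medical events, "particularly moderate exacerbations treated with antibiotics and/or steroids". The visit descriptions in section 8 and the monthly telephone contacts use the same description.

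SAP 7.2 gives no clinical definition. The endpoint is "the sum of the number of COPD exacerbations recorded as “Moderate” or “Severe” in the ‘COPD Exacerbation Form", and the count goes into a Poisson regression. The trial is open label, and neither document describes adjudication of exacerbations.

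**The concern.** Extra reliever is absent from the opening definition and present in the sentence that assigns the grade. The grade is what the SAP counts. A site that works from the grading sentence can label a reliever-only worsening as moderate, while a site that works from the opening definition records nothing. As-needed short-acting beta agonists may be prescribed (Protocol 6.5.1), so such episodes can be expected to occur.

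The stake is the meaning of one secondary endpoint. Staff who know the treatment arm apply the label, and no later step compares it with the treatment given. If reliever-only episodes are included, the count mixes treated exacerbations with milder worsening, and site habit or knowledge of the arm can influence the total.

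**Working it through.** **The plan's own figure.** The only sizing figure belongs to the primary endpoint (Protocol 9.2: 9% vs 15%, two-sided 5%, 80% power, 10% dropout).

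- Hazard ratio = ln(0.91)/ln(0.85) = 0.580.
- Freedman events = (1.960 + 0.842)² × (1.580/0.420)² ≈ 111.3.
- Per group = 111.3/(0.09 + 0.15) = 463.7, so 464. With dropout, 464/0.90 = 515.6, so 516.

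Both figures reproduce, and neither uses exacerbations. The documents give no exacerbation rate, effect size or power.

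**The texts side by side.** The grading sentence has no separator after the word bronchodilators. It can be read as a three-item list (reliever, corticosteroid and/or antibiotic) or as reliever together with corticosteroid and/or antibiotic. All episodes below are sustained worsening.

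| Episode | Opening definition | Grading sentence as list | Grading sentence as combination | Collection instructions |
|---|---|---|---|---|
| Extra reliever only | No event | Moderate | Not moderate | Not named |
| Systemic corticosteroid or antibiotic at home, no extra reliever | Event | Moderate | Not moderate, taken literally | Named |
| Systemic corticosteroid or antibiotic at home, with extra reliever | Event | Moderate | Moderate | Named |

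The list reading departs from the opening definition in the first row, and the combination reading departs from it in the second. Neither reading matches it in all three rows.

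**The severe sentence.** It carries the same treatment list, so a home-treated episode literally meets both grades unless the fragment on admission and death is attached to it. SAP 7.2 adds the two grades together and SAP 3.5.2 lists no separate severe endpoint, so a swap between grades leaves the count unchanged.

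**The primary endpoint.** SAP 7.1 requires an admission or a death. A reliever-only episode at home supplies neither.

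**Illustration of direction only.** Every input here is assumed.

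- Dilution: let f be the share of recorded LABD-arm events that are reliever-only, with no treatment effect on them and a true rate ratio of 0.75 on the rest. LABD-arm inflation = 1/(1 − f) − 1, which is 11%, 25% and 43% for f = 0.1, 0.2 and 0.3. Observed ratio = 0.75(1 − f) + f, which is 0.775, 0.80 and 0.825.
- Unequal labelling with a true ratio of 1.00: suppose reliever-only events are added at 10% of qualifying events in the LABD arm and 5% in the LABD+ICS arm. The observed ratio is 1.05/1.10 = 0.955. At 30% and 10% it is 1.10/1.30 = 0.846. The reverse imbalance would push the ratio above 1.

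**The case against.** The strongest reply is that 8.1.2 defines first and grades second. The opening definition says what an event is, and the later sentences only sort events that have already qualified. Read in that order, a reliever-only episode never reaches grading. The collection instructions support this: they name antibiotics and/or steroids throughout, and the schedule of activities has no reliever diary. The missing separator may be a typing slip, and the combination reading also excludes reliever-only episodes. Sites review medical records and prescribed medication as well as asking the patient.

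Much of this stands. A reader might infer that the protocol sets two irreconcilable definitions, or that reliever-only episodes will be counted. The documents do not support either inference: the text permits that count, does not require it, and leans towards the narrower meaning. A reader might also infer that the severe wording inflates the endpoint, or that the rate ratio will be attenuated by a known amount. The first fails because the two grades are summed, and the second because the documents supply none of the inputs.

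The reply does not remove the problem. The section nowhere says that the opening definition is a gate. The gate is not enforced downstream either, because the SAP counts the grade label without checking treatment. Pointing to the cited guideline does not settle the matter, since the protocol then writes out its own wording for sites to apply.

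**Conclusion.** Protocol 8.1.2 is internally inconsistent on what counts as a moderate or severe exacerbation, and SAP 7.2 passes the inconsistency into the analysis by summing site labels. Reliever-only episodes could therefore enter this secondary endpoint. The narrower meaning is the more likely intention.

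The size of any effect is unknown. It depends on how many reliever-only episodes occur, how many sites label them moderate, and whether labelling differs by arm, and the documents give no figure for any of these. The point is confined to one secondary endpoint. The primary endpoint and the 464/516 sample size are not affected, and the severe wording matters for clarity only. The conclusion assumes that the exacerbation form, whose layout is not in the documents, does not itself impose a treatment condition.

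**What to change.** **Protocol 8.1.2.** Reconcile its sentences with each other, with the collection instructions in 8.1 and with the guideline the section cites. The result should be one definition that separates moderate from severe and says explicitly whether reliever use alone qualifies.

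**SAP 7.2.** State that definition. Count only entries that meet it on recorded systemic corticosteroid or antibiotic treatment, admission or death. If form entries cannot all be linked to medication records, keep the label-based count and run the restricted count as a sensitivity analysis. This filter follows the narrower meaning and would need adjusting if the sponsor reconciles the text the other way. Settle the rule before counts by arm are examined.

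The data should largely exist already. Protocol 6.5 records each medication with its reason and dates, 8.1 records prescribed medication and hospitalisations, and SAP 7.1 takes the admission date from the same exacerbation form. The change concerns counting only and alters no patient's treatment. The cost is a wording correction, a small derivation effort and possibly slightly fewer events.

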8.1.3. Assessment of number of pneumonia events

Pneumonia events will be recorded based on the clinical diagnosis and will be confirmed by chest x-ray where possible.

8.1.4. Acute cardiac events

Acute cardiac events will be recorded based on the clinical evaluation.

Acute CV events are defined as an inpatient or emergency department visit with a primary diagnosis of any of the following conditions (International Classification of Diseases, 9th Revision, Clinical Modification (ICD-9-CM) codes are also shown). Coronary heart disease (ICD-9-CM codes 410-414), cardiac arrhythmia (ICD-9-CM code 427), heart failure (ICD-9-CM code 428), or ischemic stroke (ICD-9-CM codes 433-434) (Wang et al 2018).

8.1.5. Cardiovascular death

Cause of death will be assessed based on the coded cause of death recorded in the participant's records. Cardiovascular death will be defined as death resulting from an acute myocardial infarction, sudden cardiac death, heart failure, stroke, cardiovascular procedure, cardiovascular hemorrhage, or death due to other cardiovascular causes. (Hicks et al 2015)

8.1.6. Quality of Life

Participants will be asked to provide responses to the CAT questionnaire and the mMRC dyspnoea scale which will be completed by the investigator.

The CAT questionnaire measures the impact of COPD on the participant's wellbeing and daily life. It includes 8 questions which are rated on a 6-point scale of 0 to 5. Participants are assigned an overall score ranging from 0 to 40. Higher scores indicate a poorer quality of life.

The mMRC dyspnoea scale rates the participant's breathlessness on a scale of 0 to 4, with higher scores indicating worse symptoms.

8.1.7. Spirometry

Participants must have their diagnosis of COPD confirmed by spirometry. The key objective diagnostic criterion for COPD is a FEV1/FVC ratio <0.7 after bronchodilation. If this criterion is not met the patient cannot be recruited into the study.

The diagnostic spirometry test (to confirm the presence of COPD and eligibility to enter the study) can be performed up to three years prior to randomization. For participants who have not had a diagnostic spirometry test within the last 3 years, the spirometry test performed at the randomization visit will be the diagnostic test. The diagnostic spirometry test must be performed *not earlier than 4 weeks since last exacerbation* or discharge from hospital following hospitalization for an acute COPD episode.

All participants will undergo a pre- and post-bronchodilator spirometry test at the randomization visit, this will be the baseline value.

A spirometry test will also be performed at the end of the study (Visit 6).

Spirometry tests will be performed in accordance with ATS and ERS guidelines (Miller et al 2005). The test will be performed before and 30 minutes after bronchodilation (4 inhalations of 100 µg salbutamol).

The following parameters will be recorded:

- Forced vital capacity (FVC)
- Forced expiratory volume in one second (FEV1)
- The FEV1/FVC ratio will be calculated

8.2. Safety Assessments

Planned time points for all safety assessments are provided in the SoA.

8.2.1. Physical Examinations

- A physical examination will be performed at each visit.
- The physical examination will include, as a minimum, assessments of the skin, lungs, cardiovascular system, and abdomen (liver and spleen).
- Investigators should pay special attention to clinical signs related to previous serious illnesses.

8.2.2. Vital Signs

- Vital signs will be measured at the screening visit, random visit and at each of the follow-up visits during the treatment period (Visits 2-6).
- Blood pressure and pulse measurements can be assessed using a completely automated device or manual techniques
- Blood pressure and pulse measurements should be preceded by at least 5 minutes of rest for the participant in a quiet setting without distractions (eg, television, cell phones).

8.2.3. Electrocardiograms

- A 12-lead electrocardiogram (ECG) will be performed at the screening visit.
- If the patient is in a “stable condition” at the screening visit and has an ECG which was recorded within the last 3 months no further ECG measurements will be recorded.
- For unstable patients and patients with no previous ECG recording available, an ECG test will be performed at the screening visit.
- A 12-lead ECG will also be performed at Visit 6 which will be completed after 12 months treatment or following early withdrawal of the participant from the study.

8.2.4. Chest x-ray

- A chest x-ray taken within the last year when the participant was in a stable condition (and at least 4 weeks before the current acute COPD exacerbation) can be used for the screening assessment.
- Optionally (centre choice), for all other participants a chest x-ray will be performed at the screening visit (the chest x-ray must be performed at least 4 weeks after the most recent acute exacerbation of COPD).

- In case of suspected pneumonia occurring during the study, the investigator is invited to confirm the diagnosis with a chest x-ray.

8.2.5. Clinical Safety Laboratory Assessments

- Laboratory tests will be performed for screening purposes only.
- All tests will be performed by the local hospital laboratory.
- See Appendix 2 for the list of clinical laboratory tests to be performed.

8.3. Adverse Events and Serious Adverse Events

The definitions of an AE or SAE can be found in Section 10.3 (Appendix 3).

8.3.1. Time Period and Frequency for Collecting AE and SAE Information

All AEs (serious and non-serious) will be collected and registered by the investigator in the CRF, from the start of study treatment until the last follow up visit at the time points specified in the SoA (Section 1.3). SAEs will be collected starting from Informed Consent signature (see 8.3.2).

Investigators are not obligated to actively seek AEs after conclusion of the study participation. However, if the investigator learns of any SAE, including a death, at any time after a participant has been discharged from the study, and he/she considers the event to be reasonably related to the study intervention or study participation, the investigator must promptly notify the sponsor.

8.3.2. Monitoring of AEs

Patients will be monitored throughout the study for AEs to the study treatment. AEs will be documented and collected on an on-going basis during the treatment period and the relevant follow up period. The Investigator will instruct the patient how to communicate any AEs occurred in this period. Medical events fulfilling one or more criteria of seriousness and occurring after the informed consent has been signed, must be immediately (within maximum 24 hours) reported to the Sponsor using an SAE form (separate paper forms will be supplied to the investigators), even if the study treatment administration has not been started yet.

Serious adverse events occurring before the initiation of the study treatment, must also be recorded on the “Medical History/Current Medical Conditions” pages of the CRF (but not in the AE page).

The Investigator has to follow all AEs until resolution, stabilization, further investigation results are obtained, or the participant is lost to follow-up.

SAEs still present at the end of the study period and for the subsequent 30 days must be followed until a final outcome (that is any outcome different from “on-going”) is determined.

An AE that is initially reported as non-serious and later on meets the criteria for an SAE must be reported as an SAE as soon as the information regarding the presence of one or more seriousness criteria become known to the investigator.

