Spirometry will be performed in accordance with American Thoracic Society (ATS) and European Respiratory Society (ERS) guidelines (Miller et al 2005). The spirometry test will be performed before and 30 minutes after bronchodilation (4 inhalations of 100 µg salbutamol). The key

objective diagnostic criterion for COPD is a FEV1/FVC ratio <0.7 after bronchodilation. If this criterion is not met the patient cannot be recruited into the study.

The participant's medical history including details of COPD and CV diseases will be reviewed and updated as necessary.

Participants will be questioned about the occurrence of any pre-treatment adverse events or serious adverse events and details will be recorded on the eCRF.

The participant will be randomized to receive the study treatment for a period of 12 months. Participants in both study intervention groups will receive prescriptions for study medication, which will be collected from the local pharmacy or hospital pharmacy department. Prescription data will be captured on the eCRF. Participants will be instructed in the correct method of using the inhaler device(s).

The participant will be given a study participation card which will include details about the study and emergency contact information for the investigational site. Participants will be instructed to contact the centre in case of worsening of the clinical conditions, particularly for acute exacerbations of respiratory symptoms.

Concomitant medications will be reviewed. Doses of all COPD medications can be adjusted by the clinical investigator according to licenced dosages for COPD for each inhaled drug, at any time during the study.

Information on anti-influenza and anti-pneumococci vaccine will be recorded.

Participants will be contacted by telephone each month, by the clinical investigator or by a research staff member, to check compliance with the study procedures and treatment (including any anti-influenza and anti-pneumococci vaccinations). Information about any hospitalizations or any unexpected medical events, particularly moderate exacerbations treated with antibiotics and/or steroids will be collected.

Visit 3: Follow-up after 3 months of treatment

Participants will be asked to complete the CAT and mMRC questionnaires.

Vital signs, including blood pressure and heart rate, will be measured.

Medical history and history of COPD and CV disease will be reviewed and updated as necessary.

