8.3.4. Recording of AEs and SAEs

During the study, site personnel will evaluate and record any change in the pre-existing condition(s) and/or the occurrence of any AEs.

Subjects will be questioned for the occurrence of any new or worsening sign or symptom at each study visit. The Investigator or designee will enquire about AEs by asking non-leading questions, such as in the following examples:

At the first scheduled AE enquiry on Day 0 (pre-dose) subjects will be asked:

“How are you feeling?”

At subsequent scheduled intervals subjects will be asked:

“Since you were last asked, have you felt unwell or different from usual?”

Out of range laboratory results arising once study treatment has begun, will be reviewed by the Investigator. The Investigator will determine whether the signs and symptoms represent clinically significant changes from the subject's baseline, and if so, they should be recorded as an AE.

The Investigator will evaluate all AEs as to:

- Seriousness: See definition in Appendix 3
- Severity: See definition in Appendix 3.
- Causal Relationship to study drug: See definition in Appendix 3.
- Outcome.

All AEs, serious and non-serious, must be recorded in the AE section of the CRF. SAEs must also be reported to the Sponsor in 24 hours through the SAE form.

After the end of study period, including follow-ups, only if a SAE is believed to be related to the study drug administration should it be reported to the Sponsor.

Adverse Events causing treatment discontinuation

If a subject is withdrawn from the study as a consequence of an AE, this must be recorded and reasoned in the CRF, and the subject must be followed up until the AE outcome resolution.

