8.1 Adverse events

Definitions and data conventions

Pre-treatment adverse events

An AE will be classified as pre-treatment AE if it starts before the date of randomization (AE onset date < date of randomization).

Treatment-emergent adverse event (TEAE)

An AE will be classified as a TEAE if it starts on or after the date of randomization (AE onset date \geq date of randomization).

In case of missing or incomplete dates not allowing a direct allocation to any of the two categories of AEs, a worst-case allocation will be done according to the available parts of the onset and the end dates. The AE will be allocated to the first category allowed by the available data, according to the following order:

- TEAE
- Pre-treatment.

Serious adverse event (SAE)

A SAE is an AE judged as serious.

Adverse drug reaction (ADR)

An ADR is an AE with relationship to study treatment equal to “Yes”.

Severe adverse event (SAE)

A SAE is an AE judged as severe intensity.

Adverse event leading to study withdrawal

An AE leading to study withdrawal is an AE with action taken equal to “Drug withdrawn” or “Drug interrupted”.

Count of adverse events

Two AEs with the same Preferred Term (PT) and classified in the same category (pre-treatment AE or TEAE) will be considered as two different events when calculating the “number of events” in the tables.

Statistical analysis

Pre-treatment AEs and TEAEs will be presented separately. Pre-treatment AEs will be presented in the listings only.

The number of treatment-emergent AEs, SAEs, ADRs, severe AEs and AEs leading to discontinuation, and the number and the percentage of patients experiencing treatment-emergent AEs, SAEs, ADRs, severe AEs and AEs leading to discontinuation will be summarised by treatment group. Differences between groups will be evaluated using Chi-square test or Fisher’s exact test (if more than 20% of the cells in a contingency table have expected counts less than 5).

Title	Statistical Analysis Plan Template		
-------	------------------------------------	--	--

Code	Version	Effective Date	Page
FRM_ST03_032	02	02 Oct 2017	24 of 26

AEs will be coded using the MedDRA dictionary (version 21.0). The SOCs and PTs will be used for tabulation. The number of treatment-emergent AEs and the number and the percentage of patients with at least one treatment-emergent AE will also be presented by SOC and PT by treatment group.

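### AE-page recording starts at first dose but the SAP's analysis clock starts at randomisation, so events in between may be missing from the TEAE, pneumonia and acute cardiac counts

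*Protocol*

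**What the plan says.** **Recording rules (Protocol).** Section 8.3.1 has AEs entered in the CRF "from the start of study treatment until the last follow up visit at the time points specified in the SoA", with SAEs collected from consent. Section 8.3.2 requires an SAE form within 24 hours for any serious event after consent, "even if the study treatment administration has not been started yet". It then adds: "Serious adverse events occurring before the initiation of the study treatment, must also be recorded on the" medical history and current conditions "pages of the CRF (but not in the AE page". Section 8.3.4 gives a different instruction: "All AEs, serious and non-serious, must be recorded in the AE section of the CRF". The Visit 2 text in section 8 reads: "Participants will be questioned about the occurrence of any pre-treatment adverse events or serious adverse events and details will be recorded on the eCRF". It does not name the page.

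**Analysis rules (SAP).** Section 8.1: "An AE will be classified as a TEAE if it starts on or after the date of randomization". Section 7.2 builds the pneumonia and acute cardiac counts from coded adverse events, without an onset window, and takes the log of time on study as the Poisson offset: "Time on study (years) = (Date of patient completion or withdrawal - Date of randomization +1)/365.25". Section 5.5 tabulates entries on the history pages as medical history or concomitant disease, according to the ongoing box.

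**First dose.** Prescriptions are issued at Visit 2 and filled at a local or hospital pharmacy (Protocol 6.1 and Visit 2). SAP 5.6 takes the date of first intake from the Study Medications Log, so it is a separate date from randomisation. Neither document limits the interval between them.

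**The concern.** The protocol's AE page opens at first dose, while the SAP's follow-up clock opens at randomisation. If the dates differ and the AE page feeds the analysis, a serious pneumonia or cardiac event in between meets the SAP's TEAE definition but is not in the data that the SAP counts. Its person-time stays in the denominator. The same event, held on the history page, may be tabulated under SAP 5.5 as a pre-existing condition.

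At stake are two secondary endpoints and the safety tables. Whether ICS raises the risk of pneumonia is a named secondary objective, so that count should have one clear start date. For non-serious AEs in the gap, 8.3.1 does not require collection at all, and no SAE form exists from which to restore them.

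**Working it through.** The documents give no figure on this point, so there is none to reproduce. The check sets the rules side by side and then estimates the size.

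**1. An event after randomisation but before first dose, rule by rule**

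- Protocol 8.3.1: outside the AE registration period. If serious, it is still collected as an SAE.
- Protocol 8.3.2: if serious, on the SAE form and the history page, not on the AE page.
- Protocol 8.3.4: in the AE section.
- Visit 2 question: this covers events up to that visit, so it cannot capture one that happens afterwards.
- SAP 8.1: treatment-emergent.
- SAP 7.2: counted if it is among the coded AEs. The start at randomisation is implied by the offset, not stated for the counts.

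The site therefore has two incompatible instructions (8.3.2 and 8.3.4). Under one of them the SAP's numerator and denominator start on different dates.

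**2. Endpoints on this route**

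- Affected: TEAE and SAE tables, pneumonia count, acute cardiac count.
- Not affected: the primary endpoint, the re-hospitalisation and death count, and the exacerbation count. SAP 7.1 and 7.2 take these from the COPD Exacerbation Form and deaths.
- Patients who never take a dose are outside the Safety set and hence outside ITT (SAP 4.2.2, 4.2.3). The problem concerns only patients who start later.

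**3. Size**

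Inputs: 516 randomised per arm and one-year composite rates of 15% and 9% (Protocol 9.2). The gap *g* is an assumption. The composite stands in for serious events because no pneumonia or cardiac rates are given.

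Per arm at 15% a year, events = 516 × 0.15 × *g*/365:

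- *g* = 1 day: 77.4 × 1/365 = 0.2
- *g* = 3 days: 77.4 × 3/365 = 0.6
- *g* = 5 days: 77.4 × 5/365 = 1.1

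Both arms together at 15% and 9%, with constant hazards −ln(0.85) and −ln(0.91) per year and events = 516 × (1 − exp(−h·g)) in each arm:

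| Gap | Events in gap, both arms | Share of a 365.25-day year |
|---|---|---|
| 0 days | 0 | 0% |
| 1 day | 0.4 | 0.3% |
| 3 days | 1.1 | 0.8% |
| 7 days | 2.5 | 1.9% |
| 14 days | 5.1 | 3.8% |

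For comparison, the year is expected to yield 516 × (0.15 + 0.09) = 124 composite events. At the 30% one-year rate that the protocol quotes from the literature, applied to all 1,032 patients, the entries for 1, 3, 7 and 14 days become 1.0, 3.0, 7.0 and 14.0.

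Serious pneumonia and cardiac events are a subset of these figures. Non-serious pneumonia, and cardiac emergency visits without admission, lie outside this proxy and cannot be sized from the documents.

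**The case against.** The strongest reply is that the documents treat Visit 2 as the start of treatment. Randomisation is Day 1, inhaler training is given then, and Protocol 6.3 speaks of dispensing at study visits. The SAP also labels events before randomisation pre-treatment and plans to list them, so it expects the AE data to reach back before first dose. With a same-day start the effect is nil. This stands as a limit on size. It does not remove the conflict, because pharmacy collection makes a later start possible and the SAP itself records first intake separately.

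Three stronger readings are tempting but not supported:

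- **A reader might infer that serious events in the gap are lost.** They are not: each should be on an SAE form and a history page, and a site that follows 8.3.4 will have it in the AE section too. The outcome is uncertain, and recovery depends on a reconciliation that the SAP does not describe.
- **A reader might infer a bias between arms, because patients who must change inhaler start later.** Nothing in the documents gives prior inhaler use or start delay by arm. Inclusion criterion 3 admits patients on short-acting drugs, LABD or LABD+ICS, so either allocation can require a change. No direction can be derived.
- **A reader might apply the quoted readmission risk of up to 20% in 30 days.** That gives 516 × 0.20 × *g*/30, or 3.4 to 17 events per arm for 1 to 5 days. Protocol 2.3 explains why such literature rates were not adopted for this population. Entry is allowed up to 6 months after discharge, and 20% in a month already exceeds the 15% planned for the year.

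**Conclusion.** The point holds as an inconsistency between recording and analysis start dates, with a further contradiction inside the protocol. Followed as written, 8.3.2 can leave a serious post-randomisation event out of counts whose person-time includes it, and can place that event among the baseline conditions. Non-serious AEs in the gap may not be recorded at all.

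The likely effect is small: about 0.2 to 1.1 composite events per arm for a gap of 1 to 5 days. This rests on an assumed gap, the planned 15% rate spread evenly over the year, and the composite as a proxy for serious events. The effect would grow only if starts were commonly late. It is a minor correction, worth making because pneumonia is a stated question of the trial and the change is cheap.

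**What to change.** Use randomisation as the single start date.

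- **Protocol 8.3.1:** collect AEs from randomisation.
- **Protocol 8.3.2:** send to the history pages only SAEs with onset before randomisation, and record later ones on the AE page.
- **Protocol 8.3.4:** align its wording with these two sections.
- **SAP 7.2:** count pneumonia and acute cardiac AEs with onset on or after randomisation, matching the TEAE rule and the offset.
- **Before the database is finalised:** reconcile SAE forms and Medical History with the AE data, and move any post-randomisation event to the AE data.

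Moving the TEAE rule, counts and offset to first dose would also make the dates agree. Randomisation is the simpler choice, because the SAP already uses it for the TEAE rule and the offset and it keeps the comparison on the randomised time origin.

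The cost is a few sentences, a CRF completion note and one reconciliation. For data already collected, the SAP change and the reconciliation are enough for serious events. Non-serious events that were never recorded cannot be restored this way, and the study report should say so.
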